7.5.1. Serum Chemistry, Hematology, and Urinalysis

Clinical laboratory tests (serum chemistry, hematology and coagulation, and urinalysis) will be performed at screening, week 15, and week 16, as detailed in Table 3. Clinical laboratory tests will be performed using the central laboratory. Specific laboratory tests to be performed are provided in Table 8. Laboratory tests performed at screening may be repeated to determine patient eligibility.

7.5.2. Other Clinical Laboratory Tests

7.5.2.1. Beta-Human Chorionic Gonadotropin Tests

β -HCG tests in urine will be performed for all female patients aged 12 years or older of childbearing potential at baseline and other in-clinic visits as detailed in [Table 3](#). The β -HCG tests in serum will be performed for all female patients aged 12 years or older of childbearing potential at screening and week 15 and if clinically indicated.

For COVID-19 updates, refer to [Appendix M](#).

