- ^t For females who are postmenarchal or aged ≥ 12 years of childbearing potential. Serum test will be administered at screening and week 15, whereas a urine test will be administered at baseline and all other in-clinic visits where this test is administered.
- ^u MD-CRS parts I and II assessments are done locally at the investigational center, by the investigator, and video recorded. An EAB will confirm, at the screening visit, that choreiform movement disorder is the predominant dyskinetic movement disorder and that DCP severity represented by an MD-CRS part II score is ≥ 10 . The EAB will inform the local rater if their assessment is different than the local rater’s assessment; however, it is the investigator who determines the subject’s eligibility. All the subsequent MD-CRS ratings will be performed by the investigator and video recorded and then centrally read, in a blinded manner.
- ^v CaGI-I and PGI-I are to be completed before all other investigator-rated scales during visits where CaGI-I and PGI-I are collected.
- ^w During telephone contact, the CGI-I scale can only be done if non-recording video is available, allowing the investigator to complete the required assessment.
- ^x The children’s C-SSRS questionnaire will be presented to patients who have reached ≥ 12 years of age at screening or 11 years of age at screening but will turn 12 years of age during the study. Children 13 years of age and under must be interviewed in conjunction with the caregiver. For children over 13 years of age, parent/legally accepted representative involvement is strongly encouraged. Questions should be directed to the child, but the parent/legally accepted representative should be encouraged to add relevant information.
- ^y A full CBCL assessment (Competence Scale [Parts I to VII] and a Syndrome Scale [behavioral items]) will be performed at screening and week 15/ET. The Syndrome Scale part of the CBCL assessment only will be performed at baseline and weeks 3, 7, 9, 12, and 16/EOS.

Clinical Study Protocol Amendment 05

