13. Caregivers provide written informed consent after being assigned the role by an adult patient, or if this role is delegated by the parent/legally accepted representative of a patient who is a minor.
14. Females who are postmenarchal or ≥ 12 years of age may be included only if they have a negative beta-human chorionic gonadotropin (β -HCG) test at baseline or are sterile. Definitions of sterile, premenarchal, and postmenarchal are given in [Appendix F](#).
15. Females who are postmenarchal or ≥ 12 years of age whose male partners are potentially fertile (ie, no vasectomy) must use highly effective birth control methods for the duration of the study (ie, starting at screening) and for 30 days after the last dose of IMP. Further details are included in [Appendix F](#).

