APPENDIX C. STUDY PROCEDURES AND ASSESSMENTS BY VISIT

1. Procedures for Screening (Day -31)

The screening visit will take place not more than 31 days before the baseline visit. Screening may be conducted over 2 separate visits at the discretion of the investigator. The following procedures/assessments will be performed at the screening visit:

- patients, parent(s)/legally accepted representative(s), and caregivers must provide their respective written informed consent and/or assent (as appropriate) before any study-related procedures are performed. Assent/consent may also be provided to 2 optional ICFs:
 - [REDACTED]
 - use of patient’s study videos for future analysis of gait digital markers and release of patient’s study videos for use in publications or educational presentations
- review of eligibility criteria
- medical and psychiatric history
- demographics
- vital signs measurements (including orthostatic blood pressure) and weight
- physical examination
- neurological examination
- height
- 12-lead electrocardiogram (ECG)
- clinical laboratory tests (chemistry, hematology, and urinalysis); these tests may be repeated to determine patient eligibility
- urine drug screen; these tests may be repeated to determine patient eligibility
- cytochrome P450 2D6 (CYP2D6) genotype
- beta-human chorionic gonadotropin (β -HCG) serum pregnancy test (for females aged 12 years or older of childbearing potential)
- MD-CRS part II video recording and investigator assessment
- Clinical Global Impression of Severity (CGI-S) (global, physician rated)
- Children’s Columbia-Suicide Severity Rating Scale (C-SSRS) (Baseline/Screening)
- Child Behavior Checklist (for ages 6-18) (CBCL), full version (Competence and Syndrome)
- Extrapyrarnidal Symptom Rating Scale (subscales I and II; ESRS)
- Epworth Sleepiness Scale (for children and adolescents) (ESS)

- concomitant medications
- contact RTSM

2. **Procedures Before Administration of Investigational Medicinal Product (Baseline [Day 1±0 days])**

Patients who meet the inclusion and exclusion criteria at the screening visit will continue to the baseline visit when baseline assessments will be conducted. The investigator should review all available data to determine patient eligibility before randomizing to the study.

The following procedures/assessments will be performed at the baseline visit:

- review of eligibility criteria

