- assignment of randomization/treatment numbers after patient eligibility is confirmed based on all available visit assessments, and entry into case report form (CRF)
- vital signs measurements (including orthostatic blood pressure) and weight
- physical examination
- neurological examination
- urine pregnancy test
- MD-CRS part I video recording and investigator assessment
- MD-CRS part II video recording and investigator assessment
- Clinical Global Impression of Severity (CGI-S) (global, physician rated)
- Pediatric Evaluation Disability Inventory-Computer Adapted Test (PEDI-CAT) (activities of daily living [ADL], caregiver completed, content-balanced version)
- Cerebral Palsy module of Pediatric Quality of Life Inventory (PedsQL) (quality of life [QoL], patient/caregiver)
- Unified Huntington's Disease Rating Scale-Total Motor Score (UHDRS-TMS) assessment
- Children's C-SSRS (Since Last Visit)
- CBCL, Syndrome scale only (since last visit)
- ESRS (subscales I and II)
- ESS
- adverse events assessment
- concomitant medications
- dispense investigational medicinal product (IMP)

3. Procedures During Administration of Investigational Medicinal Product (Double-Blind Treatment Period Inclusive of Titration Period)

- a. Week 1 (day 7±1 day), week 2 (day 14±3 days total from baseline), week 4 (day 28±3 days total from baseline), week 5 (day 35±3 days total from baseline), and week 6 (day 42±3 days total from baseline)**

The following procedures and assessments will be performed at weeks 1, 2, 4, 5, and 6:

- telephone contact (with non-recording live video)
 - Clinical Global Impression of Improvement (CGI-I) (global, physician-rated)
 - assessment of IMP accountability/compliance/supply
 - adverse events assessment
 - concomitant medications
 - evaluation/adjustment of IMP dose
- b. Week 3 (day 21±3 days total from baseline) and week 7 (day 49±3 days total from baseline)**

The following procedures and assessments will be performed at weeks 3 and 7:

- vital signs measurements and weight
- 12-lead ECG
- urine drug screen (week 3 only)
- urine pregnancy test
- Caregiver Global Impression of Improvement (CaGI-I) (global, caregiver rated). The CaGI-I is to be completed before all other investigator-rated scales during visits where CaGI-I is collected.
- Patient Global Impression of Improvement Scale (PGI-I) (global, patient/caregiver). The PGI-I is to be completed before all other investigator-rated scales during visits where PGI-I is collected.

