- Children's C-SSRS (Since Last Visit)
- CBCL, Syndrome scale only (since last visit)
- ESRS (subscales I and II)
- ESS
- CGI-I and CGI-S (global, physician rated)
- dispense/collect IMP

During the week 3 visit, the last dose bottle is to be returned to the patient in order to take 1 last tablet in the evening to complete the week 3 dosing for that day. Refer to the pharmacy manual for further details.

- assessment of IMP accountability/compliance/supply

- adverse events assessment
- concomitant medications
- evaluation/adjustment of IMP
- contact RTSM

4. Procedures During Administration of Investigational Medicinal Product (Maintenance Period)

a. Week 9 (day 63±3 days total from baseline) and week 12 (day 84±3 days total from baseline)

The following procedures and assessments will be performed at weeks 9 and 12:

- vital signs measurements and weight
- urine drug screen (week 9 only)
- urine pregnancy test (week 12 only)
- MD-CRS part I video recording and investigator assessment
- MD-CRS part II video recording and investigator assessment
- CaGI-I (global, caregiver rated)
- CGI-I and CGI-S (global, physician rated)
- PGI-I (global, patient/caregiver)
- UHDRS-TMS
- Children's C-SSRS (Since Last Visit)
- CBCL, Syndrome scale only (since last visit)
- ESRS (subscales I and II)
- ESS
- dispense/collect IMP
- assessment of IMP accountability/compliance/supply
- adverse events assessment
- concomitant medications
- contact RTSM

b. Week 15 (day 105±3 days total from baseline) or early termination (ET)

The following procedures and assessments will be performed at week 15 or ET:

- vital signs measurements (including orthostatic blood pressure) and weight
- physical examination
- neurological examination

- height
- 12-lead ECG
- [REDACTED]
- clinical laboratory tests (chemistry, hematology, and urinalysis)
- urine drug screen
- β -HCG serum pregnancy test (for females aged 12 years or older of childbearing potential)
- MD-CRS part I video recording and investigator assessment
- MD-CRS part II video recording and investigator assessment
- CaGI-I (global, caregiver rated)
- CGI-I and CGI-S (global, physician rated)
- PEDI-CAT (ADL, caregiver completed, content-balanced version)
- PedsQL (QoL, patient/caregiver)
- PGI-I (global, patient/caregiver)
- UHDRS-TMS
- Children's C-SSRS (Since Last Visit)
- CBCL, full version (since last visit) (Competence and Syndrome)
- ESRS (subscales I and II)
- ESS
- collect IMP

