APPENDIX F. BIRTH CONTROL METHODS AND PREGNANCY TESTING

Females of childbearing potential are defined as the following:

- not surgically (documented hysterectomy, bilateral oophorectomy, or bilateral salpingectomy) or congenitally sterile
- postmenarchal or ≥ 12 years of age

Females who are not of childbearing potential are defined as the following:

- premenarchal or being in the period of a female's life before the first menstrual period occurs

Highly effective birth control methods:

Highly effective birth control methods are methods that can achieve a failure rate of less than 1% per year when used consistently and correctly are considered. Such methods include the following:

- Combined estrogen and progestogen hormonal contraception (oral, intravaginal, and transdermal) associated with inhibition of ovulation; these should be initiated at least 1 month (for IMPs potentially teratogenic/genotoxic) before the first dose of IMP
- Progestogen-only hormonal contraception (oral, injectable, and implantable) associated with inhibition of ovulation; these should be 1 month (for IMPs potentially teratogenic/genotoxic) before the first dose of IMP
- Intrauterine device and intrauterine hormone-releasing system need to be in place at least 2 months before screening
- Bilateral tubal occlusion
- Vasectomized partner, provided that he is the sole sexual partner and has received medical assessment of the surgical process
- Sexual abstinence is **only** considered a highly effective method if defined as refraining from heterosexual intercourse in the defined period. The reliability of sexual abstinence needs to be evaluated in relation to the duration of the clinical study and the preferred and usual lifestyle of the patient.
- Periodic abstinence (eg, calendar, ovulation, symptothermal, and post-ovulation methods), declaration of abstinence for the duration of a study, and withdrawal are **not** acceptable methods of contraception (according to Medicines and Healthcare Products Regulatory Agency).

Unacceptable birth control methods:

Periodic abstinence (calendar, symptothermal, and post-ovulation methods), withdrawal (coitus interruptus), spermicides only, and lactational amenorrhea method are not acceptable methods of contraception. Female condom and male condom should not be used together.

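### Section 7.5.2.1 and the Appendix C serum entries limit pregnancy testing to age 12 and over, while criterion 14, Table 3 and Appendix F also cover postmenarchal girls under 12

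*Protocol*

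**What the plan says.** **Narrower population (age floor of 12).** The Protocol states this five times.

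- Section 7.5.2.1, urine sentence: testing "will be performed for all female patients aged 12 years or older of childbearing potential at baseline and other in-clinic visits".
- Section 7.5.2.1, serum sentence: "tests in serum will be performed for all female patients aged 12 years or older of childbearing potential at screening and week 15", and also when clinically indicated.
- Appendix C, at screening, at week 15/ET and at unscheduled visits: "serum pregnancy test (for females aged 12 years or older of childbearing potential".

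**Wider population (menarche reached, or age 12 and over).**

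- Section 4.1, criterion 14 (repeated in the synopsis) applies to females who are postmenarchal or at least 12. They "years of age may be included only if they have a negative beta-human chorionic gonadotropin" test at baseline, or are sterile.
- Table 3, footnote t, which governs the β-HCG row, opens "For females who are postmenarchal or aged" and goes on to the same age of 12.
- Appendix F defines childbearing potential as not being sterile and being "postmenarchal or ≥ 12 years of age".

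**No population stated.** The Appendix C urine entries at baseline and at weeks 3, 7, 12 and 16 say only "urine pregnancy test", in one case with a note restricting the test to week 12.

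Criterion 1 admits patients from age 6.

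**The concern.** Menarche can come before age 12, and the words on menarche in criterion 14, footnote t and Appendix F have a purpose only for girls in that position. Section 7.5.2.1 and the Appendix C serum entries drop those words and keep the age. A site that works from the dedicated β-HCG section or from the visit-by-visit checklist could therefore omit tests that the eligibility criteria and the schedule require.

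The result is used in several places. A negative baseline test is a condition of entry under criterion 14, and pregnancy is an exclusion. A positive test during the study leads to withdrawal (Section 4.3) and to stopping the investigational product (Section 7.3). Under the COVID-19 provisions in Appendix M, failure to complete the week 3 or week 7 safety assessments in time leads to early termination. Those assessments include β-HCG where it is relevant, and whether it is relevant for this girl depends on which population statement the site follows.

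This is a matter of safety and eligibility. It does not touch the estimand, the analysis sets or the error rate.

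**Working it through.** No figure in the plan has to be reproduced. The check has three parts.

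**1. The statements side by side**

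| Place in the Protocol | Tests covered | Population | Postmenarchal girl under 12 |
|---|---|---|---|
| 4.1, criterion 14 | baseline test for entry | postmenarchal or 12+ | included |
| Table 3, footnote t | whole β-HCG row | postmenarchal or 12+ | included |
| Appendix F | definition | not sterile, and postmenarchal or 12+ | included |
| 7.5.2.1, urine | baseline, other in-clinic visits | 12+ and of childbearing potential | outside |
| 7.5.2.1, serum | screening, week 15, if clinically indicated | 12+ and of childbearing potential | outside |
| Appendix C, serum | screening, week 15/ET, unscheduled | 12+ and of childbearing potential | outside |
| Appendix C, urine | baseline, weeks 3, 7, 12, 16 | none stated | not settled |

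**2. What the age floor does**

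By Appendix F, childbearing potential means not sterile and (postmenarchal or aged 12+). Section 7.5.2.1 adds the condition aged 12+. The combination reduces to not sterile and aged 12+.

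Subtracting the second set from the first leaves not sterile, postmenarchal and under 12. Every non-sterile female of 12 or more already meets the Appendix F definition, so the added age removes nobody else. Criterion 1 makes girls aged 6 to 11 eligible, so the removed group lies inside the trial population.

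**3. Number of tests for one such girl**

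The β-HCG row of Table 3 is marked at screening, baseline, and weeks 3, 7, 12, 15/ET and 16/EOS, which makes 7 scheduled tests. A discretionary test at unscheduled visits comes on top. Footnote t assigns them as follows:

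- serum: screening and week 15 = 2
- urine: baseline and weeks 3, 7, 12 and 16 = 5
- 2 + 5 = 7

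What each place requires for her:

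- Table 3 with footnote t: 7 of 7
- Section 7.5.2.1 as worded: 0 of 7
- Appendix C: 0 of 2 serum, and 5 urine tests with no stated population

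The amendment log for Amendment 02 records that an age phrase was deleted from the Appendix F definition. That fits leftover wording in Section 7.5.2.1 and Appendix C, but the finding rests on the current text alone.

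**The case against.** The strongest reply is that the two wordings can be obeyed together. Section 7.5.2.1 says whom to test and does not say that only those may be tested. Its population is a subset of the one in footnote t, so a site that follows footnote t meets both. The urine sentence also refers to Table 3, where the reader finds the footnote. On this view, 0 of 7 counts wording and does not predict missed tests.

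The entry gate also holds. Criterion 14 bars a postmenarchal girl of any age without a negative baseline test unless she is sterile. The Appendix C baseline urine entry carries no age limit, and eligibility must be confirmed before randomization. On Appendix C's own wording the exposed tests are the two scheduled serum tests and a discretionary one, and the screening serum test is followed by the baseline urine test.

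Much of this stands. She remains covered by criterion 14 and footnote t, and 0 of 7 describes what Section 7.5.2.1 says when read by itself. Two things do not stand. The reference to Table 3 qualifies the visits and not the population, and the serum sentence makes no such reference for its population or visits. And the Appendix C parentheses read as limits on who is tested, so a site using them as a checklist has no prompt to look elsewhere.

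One further remark is fair but separate. Appendix F puts a premenarchal girl of 12 or more both among those of childbearing potential and among those who are not. The change proposed here neither causes nor resolves that.

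**Conclusion.** The concern holds. Five current statements set an age floor of 12 for pregnancy testing, and three current statements use a wider population. The only group affected is non-sterile postmenarchal girls under 12.

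For each such girl, 7 scheduled tests are in question under Section 7.5.2.1, and 2 serum tests under Appendix C. The total effect cannot be given: the Protocol states neither the sex distribution nor menarche status, about 65 patients are planned overall, and the number concerned may be zero or very few.

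The conclusion rests on reading the age condition and childbearing potential as joint requirements, and childbearing potential as Appendix F defines it. The matter is minor in weight. It is still an error in an operative safety instruction, and it is worth correcting at the next amendment.

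**What to change.** In both sentences of Section 7.5.2.1 and in the three Appendix C serum entries (screening, week 15/ET, unscheduled), replace the age-limited phrase with: *of childbearing potential (postmenarchal or ≥12 years; Appendix F)*. Add the same qualifier to the Appendix C urine entries at baseline and at weeks 3, 7, 12 and 16, so that every entry names its population.

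The cost is wording only. No test or visit is added, because Table 3 already schedules all of them for this group.

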7.5.2.2. Urine Drug Screen

A urine drug screen will be performed at the time points specified in [Table 3](#). A urine drug screen performed at screening may be repeated to determine patient eligibility.

The urine drug screen detects the presence of drugs of abuse. Additionally, the urine drug screen will detect the presence of drugs prohibited according to the laboratory manual. If a given parameter cannot be tested using urine, or if the investigator considers that additional testing is needed, an alternative matrix (eg, serum) may be considered acceptable. Such tests may be performed locally. The sponsor's medical expert must be made aware in advance of, and provide approval for, drug screen parameters to which this will apply.

A positive result for any drugs of abuse or their metabolites or drugs prohibited according to the laboratory manual, without medical explanation, will preclude the patient from randomization/enrollment or continued participation in the study. Some of the drugs listed in this urine drug screen may be permitted in certain cases when the particular medication is being used under a physician's or clinician's guidance and in compliance with the physician's or clinician's recommendation for a specific condition (for example, phenobarbital [barbiturates] for seizures, stimulant medications [including amphetamine, methylphenidate, and lisdexamfetamine] for attention deficit hyperactivity disorder, and opiates or oxycodone for pain) and if the dosing has been stable for at least 4 weeks before screening and no changes to dose or frequency are anticipated during the course of the study. Such cases should be discussed with the medical monitor. Patients who either are using these medications or have a positive drug screen for these substances or derivatives should be submitted to the medical monitor for consideration of participation in this study. Patients with a substance use disorder are excluded from this clinical trial. However, if per the investigator's judgment, a patient does not meet the criteria for substance use disorder, a positive drug screen result for these medications or derivatives, without medical explanation, should be discussed on a case-by-case basis with the medical monitor to determine the patient's eligibility, based on the information available.

For COVID-19 updates, refer to [Appendix M](#).

7.6. Physical Examination

Physical examinations, including height and weight, general appearance, skin, head, eyes, ears, nose, throat, neck, lymph nodes, cardiovascular, respiratory, musculoskeletal, abdominal, and extremities will be performed at the time points detailed in [Table 3](#).

Weight must be measured with shoes and outerwear off.

Any new physical examination finding (ie, since the screening visit) that is judged by the investigator as clinically significant will be considered an adverse event, recorded on the CRF, and monitored as described in Section 7.1.2.

Investigators should pay special attention to clinical signs related to previous serious diseases.

